AURORA HEALTH CARE, INC.

PROTOCOL TITLE: Pilot study for the efficacy and tolerability of Senokot-S[®] in the treatment of diabetic gastroparesis

PRINCIPAL INVESTIGATOR:

[name] Hospitalist [name] [contact] [contact] Email: [contact]

INVESTIGATORS AND KEY PERSONNEL:[name], [name], [name]

This protocol was designed and developed by Aurora Healthcare, Inc. It is intended to be used only in conjunction with institution-specific IRB approval for study entry.

I. Background and Significance

Diabetic gastroparesis can be a difficult-to-treat complication of longstanding diabetes that can significantly compromise quality of life in those affected. Today there is only one medication approved by the FDA for the indication of diabetic gastroparesis and it has received a black box warning due to potential for severe neurological side effects. There are other medications that have found some success in the treatment of diabetic gastroparesis, but they also have the potential for serious side effects, and some are only available through a special use program.¹

II. Specific Aim

The aim of the study is to evaluate the efficacy of the stimulant laxative Senokot-S[®] for the treatment of diabetic gastroparesis. Senokot-S, and its metabolites, are thought to produce peristalsis, drive intra-luminal fluid and electrolyte shifts, and have an irritant effect on the gut mucosa^{2,3}. These complex physiologic mechanisms appear may sufficiently promote stomach emptying, and thereby reduce or eliminate the severity of gastroparesis symptoms. In this open label study, participants will be randomized into high and low dose groups to assess for ideal dosing and tolerability. It is the overall goal of this study to select the most promising dose-strength for the treatment of mild through severe gastroparesis.

(c) Study End Points

- a. Primary Endpoint
 - i. Modified GCSI-DD: Subjects will complete the modified Gastroparesis Cardinal Symptom Index-Daily Diary (mGCSI-DD)^{4,5}. The mGCSI-DD is a validated patient reported outcome (PRO) instrument with excellent testretest reliability, and will be used as the primary instrument to assess for efficacy in this study.
 - ii. Questions on the mGCSI-DD are a 6-point Likert scale from 0 (none) to very severe (5) that address: nausea, retching, vomiting, stomach fullness, ability to finish a normal-sized meal, feeling excessively full after meals, loss of appetite, bloating, external assessment of stomach size, upper ab-dominal pain or discomfort.
- b. Secondary Endpoint
 - i. Breakthrough medication use: Defined as the change in the frequency of use of breakthrough medication, which is the medication that has been previously prescribed on an as-needed basis to manage symptoms.

Any change in frequency of use of breakthrough medications will be used as a secondary endpoint to assess for efficacy in the study.

 Bowel habits: Subjects will self report bowel habits during the baseline week and through the study period on the same questionnaire form. Since Senokot-S functions primarily as a mild bowel stimulant any significant change in bowel habits will help to assess for tolerability in this study.

IV. Study Design

The Phase II study design will be an open label, pre- and post-treatment assessment, prospective study. Sixty (60) study participants will be recruited over a 5-month period at a single site. Participants will be randomized into two treatment groups, a high- and low-dose, and will take medication dosed orally, twice daily or once daily at night.

V. Experimental Design, Methods, and Study Procedures

- **a.** Initial Identification of Potential Study Subjects Gastroenterologists who have agreed to refer their patient with diabetic gastroparesis for this study will make the initial contact with those patient (study inclusion/exclusion criteria will be provided to these physicians for ready reference). If the patient is interested in participating in the study the gastroenterologists will secure the patient's verbal permission to provide their name and contact information (phone or e-mail) to [name] or another member of the study team. The study team member will contact the patient and arrange a time to meet with them to explain the study and to answer any questions the potential subject may have.
- b. Screening Visit The screening visit will include reviewing the participants' complete medical history after reviewing and obtaining informed consent. Data from the participant's medical history will be abstracted from the electronic medical record (EMR) and will be securely stored with other study-related data. Participants will be given the mGCSI-DD questionnaire and instructed on its use. At this visit participants will start recording their week of baseline scores by filling out a separate mGCSI-DD questionnaire and Breakthrough Medication Use and Bowel Habits documentation form daily.
- c. Visit 1 will occur 1 week after the screening visit. Participants will return with their mGCSI-DD baseline week of scores. They will be sequentially randomized (1:1) into either the high (8.6/50mg of senna/docusate taken by mouth twice daily) or low (8.6/50mg of senna/docusate taken by mouth once every night) dose study group. To reduce potential subject bias and placebo effect, participants will not be informed as to which dose of study medication they are randomized. They will be given their study medication and their 28-day mGCSI-DD questionnaire sheets, along with a pre-printed return envelope for use after completing their month of treatment in the study. They will be instructed to decrease use of any previously prescribed breakthrough medication as can safely be tolerated. Examples of these medication may include prokinetics such as Reglan (metoclopramide), erythromycin, or domperidone; anti-emtics such as Zofran (ondansetron), or Compazine (prochloperazine); or analgesics such as tramadol,

hydrocodone, or oxycodone. They will also be instructed to resume any breakthrough medication use as previously prescribed at the completion of the study and to continue routine follow ups with their care providers.

Subjects will be instructed to immediately contact the Principal Investigator if they experience episodes of significant diarrhea or rectal bleeding.

Participants may be notified by phone at the end of their study period to verify data or request missing data.

VI. Risks

Senokot-S side effects. Known side effects of Senokot-S include diarrhea, nausea or vomiting, stomach pain, rectal bleeding, gas, abdominal bloating, and potential for allergic reaction such as skin rash. There have been safety concerns in the past about potential complications from long term use of stimulant laxatives like Senokot-S, such as cathartic colon, increased incidence of colorectal cancer, and liver disease. Several recent studies and reviews refute those previous conclusions and suggest long-term use of mild stimulant laxatives is likely safe when needed^{3,6,7}. Senokot-S is listed as pregnancy category C by the FDA. Women with child bearing potential will be required to use an effective form of birth control while participating in this study.

Ineffective treatment of diabetic gastroparesis. Since this medication has not yet been studied in the treatment of diabetic gastroparesis it is possible that symptoms of the disorder may worsen. The common symptoms of diabetic gastroparesis include nausea, vomiting, postprandial fullness, early satiety, and abdominal pain.

Loss of confidentiality. It is expected that this risk will be low because of numerous safeguards that will be in place, including standard data management procedures with Aurora Health Care.

VII. Benefits

A successful outcome in the proposed study will have immediate implications by reducing the symptoms of diabetic gastroparesis. Such a result will address the significant unmet need by providing a safe, inexpensive pharmacological therapy for a difficult to treat chronic disorder. These findings would allow patients to reduce or eliminate intake of the only FDA-approved therapeutic medication, Reglan[®], which has a black box warning and unfavorable side-effect profile. These known potential benefits are highly likely to outweigh the potential risks of the intervention in this study.

VIII. Study Population

Inclusion Criteria:

- Age 18-75 years, male and non-pregnant, non-lactating females
- Diagnosis of type 1 or type 2 diabetes mellitus
- Clinical diagnosis of diabetic gastroparesis

Exclusion Criteria:

- Diagnosed idiopathic gastroparesis
- A history or inflammatory bowel disease, such as Crohn's disease or ulcerative colitis
- A history of bowel obstruction, current unexplained abdominal pain, or undiagnosed rectal bleeding
- Gastrointestinal cancer
- Any active cancer
- Prior gastric surgery
- End-stage heart disease, liver disease, lung disease
- Known or suspected drug abuse
- Any condition requiring use of daily narcotics
- Concurrent usage of mineral oil or products containing mineral oil
- Current or recent (within the last 3 months) usage of Senokot-S, docusate or senna

IX. Recruitment and Screening

Recruitment will occur through care provider referrals. Clinicians will be notified of the study through paper advertisement and posters. Initial screening will be done over the phone or through e-mail at the time of referral and will include a medical record review. Final screening and informed consent will be completed during the formal in person screening visit between the participant and research staff and is expected to take about one to two hours.

X. Privacy Plan

Patients will initially be notified of the potential to be in a research study by a current caregiver. If the patient is agreeable to consideration for the study the research team will be contacted by phone or through e-mail by the clinician with the patient's contact information. The patient will then be contacted by a member of the research team via an institution-based phone or EMR e-mail (based on the patient's preference) for initial screening and to set up a clinic visit for final screening and informed consent.

XI. Data Collection

The data to be collected will include a complete medical history of the participant, mGCSI-DD score forms, medication usage and bowel habits forms. Data will not be shared with any outside institutions.

This research study plans to store and manage the subject lists, demographic information, validated questionnaire, study and breakthrough medication use, and bowel habits datasets in REDCap Cloud, a secure electronic data capture application that is based on Vanderbilt University's REDCap application. Flexible for a variety of types of research, REDCap Cloud provides an intuitive data-entry interface for end users into study-specific data collection forms associated with study events. The application includes real time validation rules and query management, audit trails, and the automated export of study data into statistical programs. The REDCap Cloud platform is compliant with GCP predicate rule requirements and US FDA 21 CFR Part 11 pertaining to the use of electronic records and signatures. Aurora Health Care, Inc. has executed an agreement for use of the application with nearly all research studies conducted at Aurora.

Access to data housed in REDCap Cloud and associated with this research study will be limited to those individuals listed on the IRB approved research study, as well as caregivers from Research Analytics for administrative reasons. Study team members access to the system and the data itself will be limited in accordance with need (i.e., biostatisticians may be limited to simply export the dataset to statistical tools, research coordinators may be limited to entering data, etc.). Overall, limiting access to study team members by need should reduce the risk of accidental disclosure and breach of confidentiality. However, using a cloud-based application may incidentally raise the risk of a breach in confidentiality, and, therefore, Aurora Health Care, Inc. has negotiated strong protections with the vendor in the event of a breach of confidentiality.

XII. Statistical Plan

All category and continuous variables will be described using appropriate descriptive statistics such as frequency, percentage for category variables and mean, standard deviation, median, and range for continuous variables. Pre and post outcomes variables for two groups of patients in the experimental groups will be compared using appropriate parametric and/or non parametric statistical tests. For all statistical tests an alpha level of 0.05 will be used and all statistical analysis will be carried out using SAS version 9.4, SAS Institute, Cary, NC.

XIII. Monitoring Plan

Data monitoring, safety monitoring, and statistical analysis will be done through the research office and principal investigator.

Participants can stop the study at any time for any reason and can resume previous treatments whenever needed. Stopping points will be at the end of the 5 month study period or if a negative trend in mGCSI-DD post-treatment scores is observed.

XIV. Regulatory Requirements

The investigators and all key personnel agree to abide by the determinations of the Aurora IRB, including obtaining documented informed consent prior to inclusion of any individual in this research study. The investigators and all key personnel will comply with reporting requirements as outlined in the Aurora IRB Standard Operating Procedures (SOPs). In addition, investigators will permit access for on-site monitoring by representatives of the Aurora IRB, the Aurora Research Institute Investigator-Initiated Research unit, and the Aurora Research Institute Quality Improvement Program.

XV. References

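### The breakthrough-medication endpoint leaves out symptom drugs first started after Visit 1, so a switch to a new drug is scored as a reduction

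*Combined protocol and SAP*

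**What the plan says.** Under Study End Points, the Secondary Endpoint on breakthrough medication is the change in how often such medication is taken. The drug that counts is defined as the one "which is the medication that has been previously prescribed on an as-needed basis to manage symptoms". The role of the endpoint is explicit: "Any change in frequency of use of breakthrough medications will be used as a secondary endpoint to assess for efficacy in the study".

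Section V.c (Visit 1) uses the same restriction: "They will be instructed to decrease use of any previously prescribed breakthrough medication as can safely be tolerated". There it refers to drugs held before study treatment begins, and that is the natural reading of the endpoint too.

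Other sections bear on drugs started later:

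- Section VI says of the disorder that "it is possible that symptoms of the disorder may worsen". It also lists nausea or vomiting, stomach pain and abdominal bloating among the side effects of the study drug.
- Section XIII says participants "can resume previous treatments whenever needed". It is silent on new treatments.
- The disease criteria in section VIII are diabetes and "Clinical diagnosis of diabetic gastroparesis". No as-needed prescription is required for entry, and no exclusion bars the start of a new symptom drug during treatment.
- Section XII leaves the tests open. It gives no unit for frequency, no analysis set, and no rule for participants without a prior as-needed prescription.
- Section V.b names a daily medication-use form for the baseline week. Its content is not shown.

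**The concern.** An endpoint meant to show relief should register a participant who needs a new drug because symptoms got worse. As defined, this one does not. If an antiemetic is first prescribed or bought in week 2, its use is not counted. If it replaces an older drug, the record shows a fall, which reads as efficacy. Participants have been told to cut down the old drug, so a switch looks just like the intended result.

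New starts are foreseeable: the protocol expects that some participants may get worse, and several listed side effects of the study drug are symptoms that breakthrough drugs treat.

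Of the listed endpoints, this is the only one that measures medication use. Section VII argues that success would let patients cut down or drop metoclopramide. Under the present definition, a participant moved from metoclopramide to a newly prescribed drug would count in favour of that argument.

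**Working it through.** The plan gives no figure for this endpoint (no baseline frequency, expected change or rate of new prescriptions), so there is none to reproduce.

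**Inputs.** From the documents: 60 participants (section IV), allocated 1:1 (section V.c), so 60/2 = 30 per arm; a baseline week, then 28 days of treatment. Every use rate and share below is assumed.

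**1. Direction for one participant.** Let O0 and O1 be weekly uses of previously prescribed drugs at baseline and on treatment, and N1 the weekly uses of drugs first started after Visit 1. Those drugs have no baseline use.

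- Counted change = O1 − O0
- Change in all symptom drugs = O1 + N1 − O0
- Counted minus all-drug change = −N1, which is never positive

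The omission therefore pushes the pre/post change one way only, towards a larger fall. Example of a full switch: O0 = 3, O1 = 0, N1 = 3. The counted change is −3 and the all-drug change is 0.

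**2. Size in one arm.** If k of 30 participants switch 3 uses a week, the arm mean moves by −3k/30.

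| k | Shift (uses/week) |
|---|---|
| 1 | −0.1 |
| 3 | −0.3 |
| 6 | −0.6 |

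More generally, if a share w starts a new drug at u uses a week, the missed use is w × u. With an assumed counted change of −2 uses a week:

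| w | u | Missed, w × u | Change including new drugs |
|---|---|---|---|
| 5% | 3 | 0.15 | −1.85 |
| 10% | 7 | 0.7 | −1.3 |
| 20% | 7 | 1.4 | −0.6 |
| 30% | 7 | 2.1 | +0.1 |

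**3. High versus low dose.** The error in the between-arm difference is −(mean N1 in the high arm − mean N1 in the low arm). It is zero if the two means are equal. With 3 switchers in the high arm and 1 in the low arm, at 3 uses a week, it is −0.3 − (−0.1) = −0.2 use a week, in favour of the high dose. With the arms exchanged, the sign reverses.

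**4. Would an analysis of baseline users only help?** Assume two-sided 0.05, 80% power and SD 1 among users. The detectable difference is √(2/30) × (1.960 + 0.842) = 0.723 SD. Suppose 30% of each arm could show no change and were scored zero.

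- All participants: the mean difference is 0.7 × 0.723 = 0.506. The variances are 0.7 × (1 + 0.723²) − 0.506² = 0.810 (high) and 0.700 (low). The SE is √(1.510/30) = 0.224, and power is 61.7%.
- Users only, 21 per arm: the SE is √(2/21) = 0.309, and power is 65.0%.

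The restriction gains 65.0 − 61.7 = 3.3 points on these inputs. Most of the loss from 80% comes from having fewer informative participants.

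**The case against.** Several points on the other side have force.

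- **Outside prescribing during treatment is not documented.** Section V.c tells participants "to continue routine follow ups with their care providers", but the sentence also covers what to do at study completion and reads most naturally as an end-of-study instruction. This stands, and the point does not rest on it. It rests on the definition, on the acknowledged chance of worsening, and on the absence of any bar on new drugs.
- **The daily form may record new drugs.** It may, since its content is not shown. One cannot say that the data will be missing. The definition would still exclude them from the endpoint.
- **Worsening is not invisible.** All participants complete the primary symptom diary daily, and this is a secondary endpoint in a pilot. That limits the weight of the point but does not correct the endpoint.
- **Both arms take the drug and the goal is dose selection.** A reader might infer that the gap always favours the drug. That holds for the pre/post change only; the comparison of doses is affected only if new starts differ by arm.
- **The instruction to cut down also drives this endpoint.** Part of any fall may simply reflect it. That is a separate matter and does not remove this one.

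A stronger reading is also tempting. Section VIII requires no as-needed prescription and section II aims to "select the most promising dose-strength for the treatment of mild through severe gastroparesis", so a reader might infer that participants without a prescription are entered as no change and dilute the effect. The documents do not say so: a score of zero, a missing value and exclusion all fit section XII. Nor does dilution follow for every measure. An individual percentage change from zero use is 0/0 and undefined, and a ratio of group means is unaffected by people who are at zero both times. Only an absolute mean change would shrink. What stands is that the rule is missing.

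**Conclusion.** The point holds for the definition. Symptom drugs first started or bought after Visit 1 are outside the endpoint, and replacing an old drug with a new one is scored as a reduction. The error in the pre/post change runs in one direction, towards apparent benefit, and equals the mean weekly use of the uncounted drugs. For the comparison of doses, its presence and sign depend on whether such use differs by arm.

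The true size is unknown. The figure of 0.1 use a week per switcher rests on an assumed 3 uses a week; the larger figures rest on assumed shares and frequencies and show only what could happen. The conclusion also rests on reading the restriction as prescribed before study treatment, which the Visit 1 wording supports. No dilution by participants without a prescription can be claimed from the documents. The primary endpoint's definition is not affected.

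**What to change.** 1. Define the endpoint as the frequency, in uses per week, of any as-needed medication taken for gastroparesis symptoms. Apply it in both the baseline week and the treatment period, and include drugs newly prescribed or bought after Visit 1.
2. Add a new-start flag to the daily form, and report the number of participants with a new start by arm.
3. Analyse absolute change in all participants, and report how many per arm had no prior as-needed prescription. Under the wider definition these participants have a defined value and can show a rise.
4. Keep any analysis limited to participants with baseline use as supportive only. It would drop people who hold a prescription but did not use it in the baseline week, and who could show a rise. Selecting on one week's use also invites regression to the mean, which favours an apparent fall.

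The cost is one reworded definition, one form column and one table line, and the estimate may be less favourable. No treatment or clinical rule changes.

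### The breakthrough-medication endpoint counts only drugs prescribed before the study, so a swap to a newly started or non-prescription symptom drug is recorded as reduced use

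*Combined protocol and SAP*

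**What the plan says.** Under Study End Points, Secondary Endpoint, breakthrough medication is defined as that "which is the medication that has been previously prescribed on an as-needed basis to manage symptoms". The same item adds: "Any change in frequency of use of breakthrough medications will be used as a secondary endpoint to assess for efficacy in the study". It states no favourable direction, unit or scoring rule.

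Section V.c (Visit 1) gives the instruction on these drugs: "They will be instructed to decrease use of any previously prescribed breakthrough medication as can safely be tolerated". Participants are also told to "resume any breakthrough medication use as previously prescribed at the completion of the study". The examples are all given as previously prescribed drugs: "Examples of these medication may include prokinetics such as Reglan (metoclopramide), erythromycin, or domperidone", followed by anti-emetics and analgesics. No non-prescription category is named.

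For recording, section V.b refers to a "Breakthrough Medication Use and Bowel Habits documentation form daily", starting in the baseline week. Section XI lists "mGCSI-DD score forms, medication usage and bowel habits forms" among the data collected, and study and breakthrough medication use among the stored datasets. The content of the forms is not given. Section XII promises only appropriate parametric or non-parametric pre/post tests at an alpha of 0.05.

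**The concern.** The set of counted drugs is fixed at entry, and participants are asked to use less of exactly that set. Someone who replaces an old as-needed anti-emetic with a new prescription or a shop-bought product shows a fall. Someone who worsens and is given an additional drug shows no rise from it. The endpoint is meant to inform efficacy, and section VII presents lower Reglan intake as a benefit, so a fall is likely to be read as a treatment effect. No untreated arm exists to show how much of a pre/post fall comes from substitution. New symptom-drug use that is not recorded at the time cannot be reliably reconstructed afterwards.

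**Working it through.** **Step 1: what is counted.** The endpoint says previously prescribed. The Visit 1 wording on decreasing these drugs and then resuming them as previously prescribed confirms that this means prescriptions in place before treatment. Nothing in sections V, VIII, XI, XII or XIII adds new or non-prescription symptom drugs to the endpoint, restricts starting them during treatment, describes a concomitant-medication log, or says how a substitution is scored. The exclusions in section VIII (mineral oil, recent senna or docusate, daily narcotics) are entry criteria and do not address this.

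**Step 2: what the rule records.** Let B be baseline weekly uses of the counted drug and s the uses moved to an uncounted drug.

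- Swap: total use goes from B to (B - s) + s = B, a true change of 0. The endpoint records (B - s) - B = -s, anywhere from 0 to -B.
- New drug added, old one unchanged: total use rises. The endpoint records 0.
- Non-prescription drug used at baseline and then stopped: total use falls. The endpoint records 0.

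The first two flatter the treatment; the third works against it. For example, with assumed values B = 7 and s = 3, the recorded change is -3 a week (-3/7 = -43%) with no true change.

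**Step 3: how large it could be.** The plan has no figure for this endpoint to reproduce.

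- From the documents: 60 participants (section IV), randomized 1:1 (section V.c), hence 30 per group; alpha 0.05 (section XII).
- Assumed: two-sided testing, so 2.5% in the favourable tail; 10-20% of participants swap 5 uses a week one-for-one; no other change in use; SD of change 3 to 6 uses a week; everyone contributes data.

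Mean recorded change = -(share x 5) = -0.5 to -1.0 uses a week. With SE = SD/√n and z = |mean change|/SE, the chance of a significant reduction is about Φ(z - 1.96).

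| SD of change | n | SE | z | Chance of a false reduction |
|---|---|---|---|---|
| 3 | 60 | 0.39 | 1.29 to 2.58 | 25% to 73% |
| 3 | 30 | 0.55 | 0.91 to 1.83 | 15% to 45% |
| 6 | 60 | 0.77 | 0.65 to 1.29 | 9% to 25% |
| 6 | 30 | 1.10 | 0.46 to 0.91 | 7% to 15% |

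If 3 is the SD without swapping, the swappers add variance: SD = √(9 + 25p(1 - p)), which is √11.25 = 3.35 at p = 0.10 and √13 = 3.61 at p = 0.20. The chances become 21-57% at n = 60 and 13-33% at n = 30. Across the assumed SDs at n = 60 the range is therefore 9-73%.

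**The case against.** The strongest reply is that the counted drugs stay available. The Visit 1 instruction goes only as far as can safely be tolerated, and section XIII lets participants go back to previous treatments whenever needed. The easiest response to worsening is to take more of the existing drug, which the endpoint records. That stands: the gap concerns newly started and non-prescription drugs, not rescue use in general.

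A reader might infer that the error runs only toward efficacy. The documents do not support that, because stopping a non-prescription drug used at baseline earns no credit and the balance depends on behaviour they do not describe.

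A reader might also infer that the dose comparison is distorted, since the protocol says "Known side effects of Senokot-S include diarrhea, nausea or vomiting, stomach pain" and one dose could prompt more new symptom drugs. This is only a possibility. Equal substitution in both groups cancels on average, no figure shows that it would differ, and the primary mGCSI-DD scores nausea, vomiting and upper abdominal pain daily in both groups, although new drugs could mask some worsening there.

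The percentages are also open to attack, and fairly. Every behavioural input is assumed. The 2.5% reference ignores that the instruction to cut down can itself produce a pre/post fall without drug effect or substitution, which is a separate problem. Section VIII does not require an as-needed prescription, so not all 60 need contribute.

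Finally, the unseen forms may already capture other drugs. Even so, the written definition would leave them out of the endpoint.

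**Conclusion.** The point holds as a defect in the definition. Applied as written, it scores a swap of s weekly uses as a change of -s and does not register a newly started symptom drug. This needs no assumption beyond the text. Treating a decrease as favourable is an inference, though a direct one from the efficacy label and section VII.

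The net direction is not certain, but a spurious fall is the main concern because participants are told to cut the counted drugs. The size is unknown. The 9-73% range at n = 60 (7-45% at n = 30) shows only that modest swapping could matter under the stated assumptions; it should not be quoted as this trial's false-positive rate. The endpoint is secondary and the scoring of the primary mGCSI-DD is untouched, so this should be corrected but does not undermine the trial as a whole.

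**What to change.** Define the endpoint as the change in frequency of use of any as-needed medication taken for gastroparesis symptoms, prescribed or non-prescription, existing or newly started. Record it daily on the existing form in both the baseline week and the 28 treatment days, with a line for any other or new symptom medication if the form lacks one. Report the total and three components: (a) previously prescribed drugs, (b) non-prescription drugs already used at baseline, and (c) drugs started during the study. State in section XII that a substitution counts in the total.

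Component (a) preserves the quantity now planned, so nothing is lost. The change affects measurement only and alters no one's treatment. It costs one definition edit, at most one form line, slightly more coding work, and possibly a less favourable figure. It needs to be in place before participants start their baseline week.
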